and derive clinical benefit will be allowed to continue emicizumab as part of this study as long as they continue to derive clinical benefit and emicizumab is still in clinical development (see Section 4.3.4). There will be an extension phase in this study for all patients who complete at least 52 weeks of treatment with prophylactic emicizumab and still deriving clinical benefit. The study will be extending for 3 years after the last Arm D patient completes 1 year of treatment *and patients still having clinical benefit are transferred to a post-trial continued access solution per Roche Global Policy on Continued Access to Investigational Medicinal Products (see Section 4.3.4). The study will end earlier, before 3 years after the last Arm D patient completes 1 year treatment, should the post-trial continued access solution be available earlier.* Those who are well controlled after 24 weeks on emicizumab (<2 spontaneous and clinically significant bleeds) will continue treatment on their assigned emicizumab regimen; whereas, those who experience suboptimal control (≥ 2 spontaneous and clinically significant bleeds) will have the option to escalate to 3 mg/kg QW per investigator's judgement after consulting with the Medical Monitor.

Figure 1 Study Schema

BR=bleed rate; mo=month.

During the study, individual bleeds will be captured as they occur, while HRQoL, health status, patient safety, and days of school or work missed will be assessed as outlined in the schedule of assessments (Appendix 1-A and Appendix 1-B). Patients (or their caregiver) will be asked via an electronic, handheld device to report their bleeds (i.e., start date and time, reason, type, location, and associated symptoms for joint and muscle bleeds) and hemophilia-related medication use (i.e., start date and time, reason, type and dose of injection). The bleed/medication questionnaire should be completed whenever a bleed or medication use occurs. In the event of no bleed or medication use, the patient should complete the questionnaire at least once a week to serve as

confirmation that no bleed or medication use occurred. In addition, health status information will be collected whenever a bleed is reported.

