However, in the ongoing Phase III Study BH29884 (adolescent and adult patients with hemophilia A with FVIII inhibitors), three thrombotic microangiopathy and three thromboembolic events were observed in 5 patients on emicizumab who concomitantly used on average, cumulative doses of >100 units/kg/24 hr for 24 hours of aPCC for the treatment of breakthrough bleeds. There was an additional thromboembolic event, which was a device occlusion without concomitant aPCC and assessed by the investigator as being unrelated to emicizumab (see [Section 1.2](#), [Section 1.3](#), [Section 5.1.2.1](#), and [Section 5.1.3](#)). Although FVIII and aPCC are fundamentally different in their potential interaction with emicizumab, investigators should keep in mind

that circulating emicizumab increases patients' coagulation potential. Therefore, it is recommended that:

- Breakthrough bleeds should be treated with the lowest FVIII or rFVIIa dose expected to achieve hemostasis, which may be lower than the patients' prior dose. Investigators should review with patients the dose to be used to treat breakthrough bleeds.
- The use of aPCC/PCC or other bypassing agents should be avoided or limited (see Section 4.4.1).
- Investigators and patients should consider objective verification of bleeds.

Also, local laboratory assessments are required to monitor the risk for thromboembolic events or thrombotic microangiopathy as per the schedule of assessments (see Section 4.5.5 and [Appendix 1-A](#)).

Patients might require dosing with FVIII or bypassing agents for the treatment of potential breakthrough bleeds, especially for the time period until steady-state concentrations of emicizum

ab have been reached. The reason for the use of coagulation products will be documented (e.g., bleeding, prophylaxis). The number of infusions needed to treat the bleed will be derived from the medication log.

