4.4.1 Permitted Therapy

Concomitant use of the following drugs and therapies will be permitted:

- Drugs intended to control bleeds, including FVIII products or bypassing agents as standard-of-care episodic treatment. Exact dosages will not be specified in the study; however, investigators should consider that circulating emicizumab may increase patients' coagulation potential. Investigators should review with patients the dose to be used to treat breakthrough bleeds. Breakthrough bleeds should be treated with the lowest FVIII or rFVIIa dose expected to achieve hemostasis, which may be lower than the patients' prior FVIII or rFVIIa dose.

Caution should be taken for patients who are using rFVIIa (e.g., consideration of using no more than 90 µg/kg of rFVIIa as an initial dose).

Use of aPCC/PCC in combination with emicizumab should be avoided completely in patients who have the option of using other bypassing agents to treat bleeds. In the event that aPCC/PCC is the only available bypassing agent, the lowest dose expected to achieve hemostasis should be prescribed, with no more than 50 units/kg of aPCC/PCC to be administered as an initial dose.

Other bypassing agents (e.g., Byclot[®]) should be avoided. In cases where such agents are the only available bypassing agent, the lowest dose expected to achieve hemostasis should be prescribed, with no more than the lowest dose described in the prescribing information to be administered as an initial dose (e.g., no more than 60 µg/kg of Byclot[®]).

Exact dose and schedule of bypassing agents should be discussed with patients at the beginning and throughout the study. Repeated dosing of rFVIIa, aPCC/PCC, or other bypassing agents should be performed only under medical supervision, which includes laboratory monitoring by additional local laboratory assessments (see [Appendix 1-A](#)), and consideration should be given to verifying bleeds prior to repeated dosing.

Caution should be taken if anti-fibrinolitics are used in conjunction with rFVIIa in patients receiving emicizumab.

- Drugs and therapies to treat adverse events and use of topical antiseptics, anesthetics, eye drops, etc., that are not considered to result in systemic exposure
- Drugs to treat an existing medical condition ongoing at study entry that do not violate the eligibility criteria (e.g., anti-retroviral therapy for HIV infections)
- Local anesthetic cream for emicizumab SC administration

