4.5.5 Laboratory, Biomarker, and Other Biological Samples

Local laboratory assessments will be performed as indicated on the schedule of assessments. When study drug administration is scheduled on days of clinic visit, laboratory samples should be drawn before the administration of study drug. Laboratory assessments will include the following:

- Hematology (hemoglobin, hematocrit, platelet count, RBC count, WBC count, absolute differential count [neutrophils, eosinophils, lymphocytes, monocytes, and basophils], mean corpuscular volume, mean corpuscular hemoglobin, mean corpuscular hemoglobin concentration, and RBC distribution width)
- Serum chemistries (sodium, potassium, glucose, blood urea nitrogen, creatinine, calcium, phosphorus, magnesium, total and direct bilirubin, albumin, alanine aminotransferase, aspartate aminotransferase, and alkaline phosphatase)

- In patients who receive bypassing agents, the following local laboratory tests will be performed within 24–48 hours of initial bypassing agent use so the investigator may monitor for potential thromboembolic events and thrombotic microangiopathy:

- Platelet count
- Serum creatinine
- Lactate dehydrogenase (LDH)
- Peripheral blood smear analysis to evaluate for schistocytes

A plasma sample should also be provided for laboratory monitoring of:

- Fibrinogen
- D-dimer

For patients who require multiple doses of bypassing agents, local laboratory monitoring should be performed every 24–48 hours thereafter until 24–48 hours following the last dose of bypassing agents administered to treat a given bleed. If applicable, laboratory results should be recorded on the Unscheduled Visit eCRFs.

- Pregnancy test: All women of childbearing potential (including those who have had a tubal ligation) will have a serum pregnancy test at screening and within 7 days prior to initiation of study medication, if applicable.

Urine pregnancy tests will be performed at specified subsequent visits. If a urine pregnancy test result is positive, it must be confirmed by a serum pregnancy test.

The following samples will be sent to the Sponsor or a designee for centralized analysis:

- Plasma samples for PK analysis
- Plasma samples for immunogenicity assessment (ADA)
- Serum and plasma for PD and exploratory PD biomarker assessments (aPTT, PT, FVIII activity, and others as listed in [Appendix 2](#))

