5.1.3 Management of Patients Who Experience Specific Adverse Events

Guidelines for management of specific adverse events are outlined in [Table 4](#).

Table 4 Guidelines for Management of Patients Who Experience Specific Adverse Events

Event	Action to Be Taken
Thrombotic Microangiopathy	
• Please see Section 3.1 and Section 3.3.3 for guidance on management of breakthrough bleeds, including required laboratory monitoring.• HCPs should be vigilant for patients who exhibit signs/symptoms consistent with thrombotic microangiopathy and immediately begin work-up and treatment, as per local guidelines.• If a patient has a thrombotic microangiopathy event, further administration of study drug should be interrupted. The decision to resume emicizumab after an event of thrombotic microangiopathy must be discussed with the Medical Monitor.
Hypercoagulation and Thromboembolic Events	
• Please see Section 3.1 and Section 3.3.3 for guidance on management of breakthrough bleeds, including required laboratory monitoring.• HCPs should be vigilant for patients who exhibit signs/symptoms consistent with thromboembolic events and immediately begin work-up and treatment, as per local guidelines.• If a patient has a thromboembolic event, administration of study drug should be interrupted. The decision to resume emicizumab after a thromboembolic event must be discussed with the Medical Monitor.
Injection-Site Reaction	
• Injection-site reactions should be treated as clinically indicated.• Emicizumab should not be injected into areas where the skin is red, bruised, tender, or hard or into areas where there are moles or scars.• In the clinic setting, patients will be monitored for signs of injection-site reactions in the period immediately following injections. Patients will be given guidance on reporting injection-site reactions when administering drug at home or after they leave the clinic.

Event	Action to Be Taken

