Appendix 1-A (cont.) **Schedule of Assessments**

- ^q See [Appendix 2-A](#) for detailed explanation of PD biomarker assessments (Sets 1 and 2). Blood samples will be banked for 5 years for future exploratory PD biomarker analyses. Blood samples may also be drawn to conduct biomarker assays at the central laboratory on an unscheduled basis (at the clinical judgment of the investigator) at any time.
- ^r Following bypassing agent treatment, patients should provide a sample for local laboratory monitoring of thromboembolic events and thrombotic microangiopathy for platelet count, serum creatinine, LDH, and peripheral blood smear analysis for schistocytes within 24–48 hours of initial bypassing agent use. A plasma sample should also be provided for local laboratory monitoring of fibrinogen and D-dimer. For patients who require multiple doses of bypassing agents, laboratory monitoring should be performed every 24–48 hours thereafter until 24–48 hours following the last dose of bypassing agents administered to treat a given bleed. If applicable, laboratory results should be recorded in the Unscheduled Visit eCRFs
- ^s At the Week 1 visit, patients or their caregivers will be trained on how to use, and be provided with, their own electronic, handheld device. At subsequent visits, as marked, investigator review of patient-reported bleed/injection questionnaire information will be conducted. Information regarding trauma events in the preceding month will be collected in the eCRF by the investigator.

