- ^h Injection-site reaction adverse events will be collected on a separate form from the adverse event form. If there is unexpected worsening of the patient's hemophilia in terms of severity (e.g., increased number of doses of FVIII to stop bleeds compared with before study entry), frequency of bleeds, or nature at any time during the study, this should be documented as an adverse event on the Adverse Event eCRF, conveying that the underlying condition has changed by including applicable descriptors (e.g., "increased clinical severity of hemophilia").
- ⁱ Drug dispensation will not occur at the study completion/early termination visit.
- ^j For patients randomized to Arm A: emicizumab 1.5 mg/kg QW subcutaneously. For patients randomized to Arm B: emicizumab 6 mg/kg Q4W subcutaneously. For patients randomized to Arm C: 6 mg/kg Q4W subcutaneously. For patients in Arm D: 1.5 mg/kg QW subcutaneously. Patients should record their actual Emicizumab administer in their handheld device.
- ^k Following bypassing agent treatment, patients are recommended to provide a sample for local laboratory monitoring of thromboembolic events and thrombotic microangiopathy for platelet count, serum creatinine, LDH, and peripheral blood smear analysis of schistocytes within 24–48 hours of initial bypassing agent use. A plasma sample can also be provided for local laboratory monitoring of fibrinogen and D-dimer. For patients who require multiple doses of bypassing agents, laboratory monitoring is recommended every 24–48 hours thereafter until 24–48 hours following the last dose of bypassing agents administered to treat a given bleed. If applicable, laboratory results should be recorded in the Un scheduled Visit eCRFs.

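### In the extension, Appendix 1-B footnote k only recommends laboratory monitoring during repeated bypassing-agent dosing, while Section 4.4.1 makes it part of the condition for such dosing

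*Protocol*

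**What the plan says.** Emicizumab continues in the extension at the assigned maintenance regimen (Appendix 1-B footnote j), and Appendix 1-B keeps a row for monitoring after bypassing agents. Its footnote k covers two situations. After first use, "patients are recommended to provide a sample for local laboratory monitoring of thromboembolic events and thrombotic microangiopathy". With repeated use, "For patients who require multiple doses of bypassing agents, laboratory monitoring is recommended every 24–48 hours thereafter". It adds that fibrinogen and D-dimer *can* also be sampled.

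Section 4.4.1 treats repeated dosing as conditional. For rFVIIa, aPCC/PCC and other bypassing agents, it "should be performed only under medical supervision, which includes laboratory monitoring by additional local laboratory assessments". The sentence is not limited to a study phase and points to Appendix 1-A.

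Other sections are also firmer than footnote k. Section 3.1 says "local laboratory assessments are required to monitor the risk for thromboembolic events or thrombotic microangiopathy as per the schedule of assessments". Section 4.5.5 says "the following local laboratory tests will be performed within 24–48 hours of initial bypassing agent use", and that repeat monitoring should be performed every 24–48 hours. Appendix 1-A footnote r says "patients should provide a sample for local laboratory monitoring of thromboembolic events and thrombotic microangiopathy for platelet count" and uses *should* again for repeat doses. Table 4 in Section 5.1.3 mentions "guidance on management of breakthrough bleeds, including required laboratory monitoring", but only as a pointer to Sections 3.1 and 3.3.3.

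**The concern.** Section 5.1.2.1 lists thrombotic microangiopathy with aPCC, and thrombosis, as identified risks. All 3 patients with thrombotic microangiopathy, and both patients with aPCC-linked thromboembolic events, had received aPCC averaging more than 100 U/kg/day for 24 hours or longer. That is sustained dosing, the setting the Section 4.4.1 condition addresses. The 50 units/kg limit on aPCC/PCC in that section applies to the initial dose only, and the section sets no cumulative limit. Supervision with laboratory monitoring is therefore its main specific control on what follows the first dose.

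An extension site working from Appendix 1-B could treat that control as optional. The routine schedule would not make up for it. Visits are 24 weeks apart, laboratory tests have a yearly minimum, and the panel in footnote g includes platelets and creatinine but not LDH or a blood smear. Bleed treatments are not collected in the extension (Section 4.5.7; Appendix 1-B footnote f), so bypassing-agent use without a sample would not routinely appear in the study data. Use followed by a sample would appear on the Unscheduled Visit eCRF.

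**Working it through.** The point rests on wording, and the plan gives no figure to reproduce. The texts side by side:

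| Place | After first use | Fibrinogen, D-dimer | Repeated doses |
|---|---|---|---|
| Section 4.4.1 | not addressed | not addressed | dosing *only* under supervision that includes laboratory monitoring |
| Section 4.5.5 | *will* | *should* | *should* |
| Appendix 1-A footnote r | *should* | *should* | *should* |
| Appendix 1-B footnote k (extension) | *recommended* | *can* | *recommended* |

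Section 3.1 says *required* without separating first from repeated use, and defers to the schedule of assessments.

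1. **Does Section 4.4.1 reach the extension?** Yes. The sentence has no phase limit, and the same paragraph has dose and schedule discussed with patients throughout the study. The hand-over in Appendix 1-A footnote d sends extension patients to Appendix 1-B for study completion and early-discontinuation follow-up. It does not lift Section 4.4.1.

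2. **Can both texts be met?** Yes, by monitoring as recommended. They part only when a site declines the recommendation: footnote k permits that, Section 4.4.1 does not. Section 4.4.1 itself says *should*, so the contrast is a restriction against an option, not *must* against *may*.

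3. **Is the first sample in the same position?** No. Section 4.4.1 does not address it. Sections 3.1 and 4.5.5 do, but both defer to the schedule of assessments, and Section 3.1 elsewhere describes safety assessment "as outlined in the schedule of assessments (Appendix 1-A and Appendix 1-B"). The softer verb in Appendix 1-B can therefore be read as the schedule those sections defer to.

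4. **Which schedule does the monitoring text cite?** In Sections 3.1, 4.4.1 and 4.5.5 the appendix cited for this monitoring is 1-A. None of the three cites Appendix 1-B at that point.

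5. **Sampling burden, for illustration.** Assume a bleed with first and last doses 48 hours apart. Sampling runs until 24–48 hours after the last dose, that is, until 72–96 hours. At 24-hour spacing the samples fall at 24, 48 and 72 hours (3 samples). At 48-hour spacing they fall at 48 and 96 hours (2 samples).

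**The case against.** The strongest reply is that only the interval is recommended. Section 4.4.1 names no interval and no tests, so a site monitoring at some other spacing would satisfy both texts. This does not hold up well: footnote k softens all three of its monitoring verbs, including the one for the first sample, where no repeat interval is involved. The footnote reads as making the monitoring itself optional.

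A second reply is that the change is deliberate. Appendix 1-B is lighter throughout: it drops ECGs, HRQoL and pregnancy tests and trims the chemistry panel. It is also the schedule written for the extension, with its own row for bypassing agents. For the first sample and for fibrinogen/D-dimer this stands, because the body text there defers to the schedule. For repeated dosing it does not settle the matter. The items dropped are fixed-timepoint assessments, whereas this monitoring is attached to giving a drug, and an intended relaxation would need an exception in Section 4.4.1.

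A third reply is that the risk is narrower than it sounds, and this also stands. No thromboembolic events were seen with emicizumab and rFVIIa alone or with single aPCC doses up to 100 U/kg (Section 5.1.2.1). Section 1.1.1 lists PCC and rFVIIa, not aPCC, as the products available in China, although Section 4.4.1 handles PCC like aPCC. The advice to avoid aPCC/PCC, the initial-dose limit and 24-hour reporting of events of special interest all remain.

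**Conclusion.** The mismatch on repeated dosing is real and should be corrected. Its practical reach is limited to extension patients given repeated bypassing-agent doses at a site that treats the recommendation as optional. That number cannot be derived. Efficacy is unaffected: the primary comparison is made once randomized patients reach 24 weeks or discontinue, and bleeds are not collected in the extension.

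Three stronger readings are tempting, and the documents do not support them:

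- **That the protocol waives monitoring in the extension.** It does not. Footnote k still recommends it, and Section 4.4.1 still applies.
- **That the first-sample wording is an equal contradiction.** Sections 3.1 and 4.5.5 defer to the schedule, so this may be a considered relaxation that the body text leaves unstated.
- **That enrolment figures size the problem.** At planned enrolment at least 30 of 85 patients have inhibitors (70 − 55 = 15, plus 15 in Arm D). That counts neither extension entrants nor users of bypassing agents.

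The conclusion assumes that no other text states an extension exception. Appendix 9 is titled for monitoring as well as dosing, but the text available here ends after the dosing guidance, so nothing is claimed about the remainder.

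**What to change.** In Appendix 1-B footnote k, change the repeat-dosing verb to *should be performed*, keeping the 24–48 hour interval and the same stopping point after the last dose as in Appendix 1-A footnote r and Section 4.5.5. Cite Appendix 1-B beside Appendix 1-A where Sections 3.1, 4.4.1 and 4.5.5 refer to this monitoring.

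For the first sample and for fibrinogen/D-dimer, the sponsor should choose: align the wording with footnote r, or state the extension exception in Section 4.5.5.

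The cost is amendment wording, a site memo and a few local blood tests that Sections 4.4.1 and 4.5.5 already call for: 2 to 3 samples in the illustrative bleed above. In small children these stay subject to the Section 3.3.6 limits of 1% of blood volume at one time and 3% over 30 days, under which safety tests take priority. The protocol gives no volume for these samples, so whether they fit must be checked for each child.

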Appendix 2-A
Schedule of Pharmacokinetic, Immunogenicity, and Biomarker Samples (Arm A, QW)^a

Schedule of Assessments—Arm A (QW)																		
	Screening	Wk 1	Wk 2	Wk 3	Wk 4	Wk 5	Wk 7	Wk 9	Wk 13	Wk 17	Wk 21	Wk 25	Q8W from Wk 33	Wk 49	Q12W from Wk 61	Daily/weekly	Study Comp./ET ^b	Safety F/U Visit ^c
PK assessment ^d		x	x	x	x	x	x	x	x	x	x	x	x	x	x		x	x
Anti-emicizumab antibodies ^e		x				x		x	x	x	x	x	x	x	x		x	x
PD biomarkers Set 1 ^{f, g}		x	x	x	x	x	x	x	x	x	x	x	x	x	x		x	x
PD biomarkers Set 2 ^{g, h}		x											x				x	x
Anti-FVIII antibodies ⁱ	x	x		x					x				x	x	x		x	x

ADA=anti-drug antibody; CWA=clot waveform analysis; ET=early termination; F/U=follow-up; FIX=factor IX; FVIII=factor VIII; FX=factor X; FXIII=factor XIII; PD=pharmacodynamic; PK=pharmacokinetic; Q2W=every 2 weeks; Q8W=every 8 weeks; Q12W=every 12 weeks; QW=every week; study comp=study completion; VWF=von Willebrand factor; Wk=week.

Note: Blood samples should always be drawn pre-dose (if taken on days of emicizumab administration); consult the Sample Handling Manual for details. In order to characterize pharmacokinetics, it is mandatory that assessments are being performed within ± 2 days of the scheduled visits.

- ^a If Arm B is switched to a Q2W dosing schedule in the future (based on emerging global data), the schedule for a QW dosing schedule is also applicable to a Q2W dosing schedule.
- ^b Study completion visit for PK, PD biomarker, and ADA sample collection is defined as when either the patient completed the study as defined in Section 3.2 or after the last patient completed 24 weeks of treatment with emicizumab, whichever occurs first. *Sample collection has stopped since March 2021.*
- ^c Anti-emicizumab antibody blood samples may also be drawn if a hypersensitivity event occurs or on an unscheduled basis (at the clinical judgment of the investigator) at any time.
- ^d Emicizumab concentration. Plasma samples for this assessment should be taken prior to injection. Patients will be dosed at the clinics (self-administration) on days where trough plasma samples are to be collected.
- ^e Anti-emicizumab antibody blood samples may also be drawn if a hypersensitivity event occurs or on an unscheduled basis (at the clinical judgment of the investigator) at any time.
- ^f Set 1: Standard aPTT, PT, FVIII activity, thrombin generation, FIX antigen, FX antigen, D-dimer, pro-thrombin fragment 1.2.

